#### **6.9.4 Timing**

AEs will be captured from the time the subject gives informed consent until the subject completes the Safety Follow-Up Visit.

Surgical procedures, planned before enrollment of the subject in the study, are not considered AEs if the condition was known before study inclusion. In this case the medical condition should be reported in the subject's medical history (see Section 6.1).

#### 6.9.5 Severity

Adverse events with changes in severity should be documented as separate events.

Intensity	Definition
Mild	Causes transient or mild discomfort; no limitation of usual activities; no medical intervention required
Moderate	Causes mild to moderate limitation in activity; some limitation of usual activities; no or minimal medical intervention or therapy is required.
Severe	Causes marked limitation in activity; some assistance is usually required; medical intervention or therapy is required; hospitalization is probable.

The term "severe" is used to describe the intensity (severity) of a specific event (as in mild, moderate, or severe); the event itself, however, may be of relatively minor medical significance (such as a severe headache). This is not the same as "serious," which is based on subject/event outcome or action criteria usually associated with events that pose a threat to a subject's life or functioning. Seriousness (not severity) serves as a guide for defining regulatory reporting obligations.

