### **6.9 Adverse Events Assessments**

#### **6.9.1 Adverse Event Definition**

In accordance with ICH and United States Food and Drug Administration (FDA) guidance, any untoward medical occurrence incurred by a subject that occurs after the first study-related procedure to the completion of the Safety Follow-Up Visit and is associated with the use of the drug, regardless of the presence of causal relationship, is a reportable AE. AEs that are ongoing at the time of the RB-US-13-0003 EOS visit will be recorded in the eCRF for this study.

All subjects participating in the study that have a EOS/ET Visit will be contacted by telephone for a safety follow-up assessment of AEs (new or ongoing) and use of any concomitant medications.

Abnormal results of diagnostic procedures, including laboratory test abnormalities, are considered AEs if they:

- Result in discontinuation from the study,
- Require treatment or any other therapeutic intervention,
- Require further diagnostic evaluation (excluding a repetition of the same procedure to confirm the abnormality), or
- Are associated with clinical signs or symptoms that would have a significant clinical impact, as determined by the Investigator.

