#### **6.9.2 Treatment-Emergent Adverse Event Definition**

A TEAE is an AE that either commenced following initiation of IMP or was present prior to the initiation of IMP, but increased in frequency or severity following initiation of treatment, regardless of causality.

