#### **6.9.3 Performing Adverse Events Assessments**

The Investigator is ultimately responsible for assessing and reporting all AEs as outlined in the protocol. The assessment of AEs may be delegated to a medically qualified Sub-investigator, trained on this study protocol, who is listed on the FDA Form 1572 or equivalent document, and on the delegation of authority form.

AEs should be volunteered by the subject or solicited from the subject using a standard statement, obtained from examination of the subject at a site visit, or from observations of clinically significant laboratory values or special examination abnormal values. If an event assessed by one of the study scales requires intervention, or if in the opinion of the Investigator, it is clinically significant, then it will be reported as an AE. Any ongoing AEs reported in the RB-US-13-0003 study will be recorded in the eCRF for this study.

All AEs are to be assessed and recorded in a timely manner and followed to resolution or until the Investigator determines that there is not an anticipated resolution. Each AE is to be documented with reference to severity, date of occurrence, duration, treatment, and outcome. Furthermore, each AE is to be classified as being serious or non-serious. In addition, the Investigator must assess whether the AE is drug-related or not.

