12.1 ADVERSE EVENTS

12.1.1 Adverse Events

Imputation rules for AE (for determination of TEAE only) start date are in Section 20.7.

Treatment-emergent Adverse Events (TEAEs)

TEAEs are those that started following the first dose of RBP-6000 and before the Treatment End Date (the maximum of the date of the end-of-study/ Early Termination (EOS/ET) visit and the date of last injection + 28 days) in this study, or were present prior to the first dose of RBP-6000 regardless of causality and increased in severity within the treatment period (defined in section 20.1) AEs include those events that are ongoing at the time a subject rolls-over from the RB-US-13-0003.

Treatment-related Adverse Events

A summary of TEAEs will be presented for the Safety Analysis Set, including the number and percentage of subjects reporting at least one TEAE, the number and percentage of subjects with the following:

- Related TEAEs
- SAEs
- Related SAEs
- TEAEs with an outcome of death
- TEAEs
- Severe TEAEs
- TEAEs leading to RBP-6000 discontinuation

A breakdown of the number and percentage of subjects reporting each TEAE categorized by SOC and PT coded per the MedDRA dictionary version 19.0 will be presented in the Safety Analysis Set. Note that counting will be by subject not by event and subjects will be only counted once within each SOC or PT.

A further tabulation of events experienced by $\geq 5\%$ of subjects by SOC and PT will be presented for the Safety Analysis Set. If there are no TEAEs experienced $\geq 5\%$ of subjects by any PT, this table will be empty.

A summary of events reported, categorized by severity, will also be provided. Subjects with multiple events within a SOC or PT will be counted under the category of their most severe event within that SOC or PT. A further tabulation of severe AE/TEAEs will be presented by SOC and PT.

Additionally, treatment-related AEs/TEAEs will be summarized by maximum severity (mild, moderate, or severe). A breakdown of severe treatment-related AEs/TEAEs by SOC and PT will be provided.

All AEs (including non-TEAEs) recorded on the CRF will be listed.

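### A carried-over adverse event that improves after Day 1 could be counted as treatment-emergent, and the SAP drops the protocol's frequency criterion without declaring it

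*Protocol*

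**What the plan says.** **Recording.** Protocol 6.9.5: "Adverse events with changes in severity should be documented as separate events". The sentence covers changes in either direction. Protocol 6.9.3 adds: "Each AE is to be documented with reference to severity, date of occurrence, duration, treatment, and outcome". Frequency is not among those items.

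**Carry-over.** Protocol 6.9.1: "AEs that are ongoing at the time of the RB-US-13-0003 EOS visit will be recorded in the eCRF for this study". Protocol 6.9.3 repeats the instruction, and SAP 12.1.1 confirms it for the analysis: "AEs include those events that are ongoing at the time a subject rolls-over from the RB-US-13-0003".

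**Protocol definition of a TEAE (6.9.2).** An event qualifies if it began after treatment was initiated, or if it "was present prior to the initiation of IMP, but increased in frequency or severity following initiation of treatment, regardless of causality".

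**SAP definition (12.1.1).** The onset criterion is "TEAEs are those that started following the first dose of RBP-6000 and before the Treatment End Date". The second criterion admits an event present before the first dose only if its severity increased within the treatment period. Frequency is not mentioned.

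**Declared changes.** Protocol 9.1 says departures from its planned analyses will be included in the SAP. SAP section 21 reports none.

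**The concern.** Every subject enters from an RBP-6000 study, so events already under way at Day 1 are a normal part of the data. The second SAP criterion shows the intent: a pre-existing event should count only if it gets worse. The recording rule in Protocol 6.9.5 can bypass that intent. If an ongoing event eases and the site opens a new record dated at the change, the onset criterion is met and recovery is counted as a new event.

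The frequency omission works the other way. A pre-existing event that recurs more often at the same severity, and is kept as one record, is a TEAE under the protocol but not under the SAP.

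TEAE incidence is the first safety variable named in SAP section 12, and Protocol 9.5.1.1 limits the safety analysis to TEAEs. The same flag feeds the relatedness, severity and special-interest tables. A carried-over event may already have been judged related to RBP-6000 in the parent study. Its milder record could then appear here as a new related TEAE.

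**Working it through.** The plan states no figure to reproduce. The check applies the two definitions to test cases.

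**Rules as written**
- Protocol 6.9.2: TEAE if (onset after first dose) or (present before, and severity or frequency increased).
- SAP 12.1.1: TEAE if (onset after first dose and before Treatment End Date) or (present before, and severity increased).

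**Test event.** For illustration, the onset is day -20 and the change is on day 40, inside the treatment period. Each case is run under two dating conventions, because the documents do not say which applies: (a) the separate record starts on the day of the change; (b) the records are linked, or keep the original onset. Each cell gives Protocol / SAP.

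| Carried-over event | (a) dated at change | (b) original onset |
|---|---|---|
| Unchanged | no / no | no / no |
| Severe to mild, or moderate to mild | **yes / yes** | no / no |
| Mild to severe | yes / yes | yes / yes |
| More frequent, same severity, one record | **yes / no** | **yes / no** |

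**Reading the table**
1. Improvement is flagged only under (a), and then under both documents. The SAP did not create this route; the protocol's onset criterion has it too.
2. True worsening in severity is captured under either convention.
3. The frequency row does not depend on dating, because no severity change occurs and no record is split. The two documents disagree outright.
4. If each record holds one severity, an increase over the pre-dose level can be seen only by comparing records. The second SAP criterion therefore needs a link between records in any case. SAP section 20 has rules for repeated assessments (20.4), missing severity or relationship (20.6) and missing dates (20.7), but none for linking.

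**Scale, by assumption only.** With about 300 subjects, one subject is 1/300 = 0.33 percentage points. The table of events in at least 5% of subjects has a threshold of 0.05 x 300 = 15 subjects. A preferred term with 14 genuine cases (14/300 = 4.7%) would enter that table with one misclassified subject (15/300 = 5.0%). If 1%, 2%, 5% or 10% of subjects had an improving carried-over event as their only qualifying record, then 300 x 0.01 = 3, 300 x 0.02 = 6, 300 x 0.05 = 15 or 300 x 0.10 = 30 subjects would be counted in error.

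**The case against.** **The start date is not stated.** Protocol 6.9.5 asks for separate events but does not say how to date them. The CRF and its completion guidelines, which might settle this, are not among the documents. A reader might infer that the protocol requires a new start date and that improvements are therefore certain to be counted. The text does not support that certainty. What stands is that a separate event with its own date of occurrence and duration is most naturally dated at the change, and that neither document says otherwise.

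**The second SAP criterion shows the intent.** Under convention (a) it would be redundant for severity changes, since every worsening would already qualify by onset. That is good evidence of what the authors meant, but it gives the programmer no rule for split records.

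**The effect may be small.** Subjects count once per system organ class or preferred term, so an extra record matters only where nothing else qualifies at that level or overall. A carried-over event already graded mild has no lower grade to step down to. A record opened on improvement to mild or moderate cannot add to the severe-TEAE tables. All events, including non-TEAEs, are listed, and no hypothesis test depends on the flag. All of this stands.

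**The frequency gap is narrow.** New episodes entered as new events after dosing still qualify by onset. Since frequency is not among the items Protocol 6.9.3 requires, the SAP may have had nothing to analyse. Even so, the departure from Protocol 6.9.2 should have been declared.

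**Conclusion.** The point holds as two limited defects.

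First, the plan does not say how split severity records of a carried-over event are dated or linked. Read literally, with the record dated at the change, an event that improves becomes a TEAE, against the intent of the SAP's second criterion. This rests on that one unstated but natural assumption.

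Second, the SAP removes frequency from the protocol's TEAE definition while declaring no change. This needs no assumption. Its effect is confined to pre-existing events that become more frequent but continue as a single record.

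The size cannot be derived from the documents. A reader might assume that 20% to 50% of subjects enter with an ongoing event and that 10% to 30% of those step down, giving 300 x 0.20 x 0.10 = 6 to 300 x 0.50 x 0.30 = 45 subjects, or 2% to 15%. The documents support neither rate. Even on those rates, the result counts subjects with any such record; it is not the error in TEAE incidence, which is smaller wherever a subject has another TEAE. Nor do the documents show that the reported rate is wrong in both directions, only that it could be. The change is still worth making, because the ambiguity affects the main safety summary and the core correction is inexpensive.

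**What to change.** 1. **SAP 12.1.1, split records.** Treat severity records of the same event as one event with its original onset. Flag a pre-existing event as a TEAE only if a post-dose severity exceeds the last pre-dose severity. This also closes, for the analysis, the gap in the protocol's onset criterion.
2. **Identifying the same event.** Use the reported term and continuity confirmed by the site and, for injection-site events, the injection site itself. Preferred term and adjoining dates alone are not enough. Protocol 5.3 alternates sides of the abdomen, so pain persisting at the last parent-study site and new pain at the Day 1 site would share a preferred term. Merging them could remove a genuine new TEAE.
3. **Frequency.** Restore the Protocol 6.9.2 wording, "increased in frequency or severity following initiation of treatment", where an increase in frequency is recorded. Otherwise declare its removal in SAP section 21, with the reason.

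**Cost.** SAP wording, a small derivation in the adverse-event dataset and a review of the linked records. Capturing frequency would also need a site or eCRF instruction. SAP 20.10 describes values already in the clinical database, so late capture may be impractical; declaring the removal needs no new data.

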#### 6.9.6 Relationship

The Investigator or a medically qualified Sub-investigator, trained on this study protocol, listed on the 1572 form or equivalent document and on the delegation of authority form is responsible for determining the AE relationship to the IMP.

The following categories will be used to define the relationship of an AE to the administration of the IMP:

Not Related: Data are available to identify a clear alternative cause for the AE other than the IMP.

Related: The cause of the AE is related to the investigational product and cannot be reasonably explained by other factors (e.g., the subject's clinical state, concomitant therapy, and/or other interventions).

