#### 9.5.1.1 Adverse Events

All AEs will be coded using the most up-to-date version of the Medical Dictionary for Regulatory Activities (MedDRA) and reported to the FDA. AEs that began after the EOS visit will not be included in the safety analysis. Only TEAEs occurring post administration of RBP-6000 will be included in the safety analysis (See [Section 6.9.2](#)).

The incidence of AEs (number and percent of subjects reporting the AE at least once during the study) will be summarized for all AEs, by the relationship to IMP and by severity.

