20.6 MISSING SEVERITY AND RELATIONSHIP TO STUDY DRUG IN ADVERSE EVENTS

If the severity is missing for an AE started on or after the date of the first dose of the investigational product, then a severity of “Severe” will be assigned.

If the relationship is missing for an AE started on or after the date of the first dose of the investigational product, then a relationship of “Related” will be assigned.

The imputed values for assessment will be used for incidence summary, while the actual values will be presented in data listings.

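### The two causality categories in Protocol 6.9.6 are not exhaustive, so an AE of uncertain cause fits neither and the related-AE tables depend on how each site resolves it

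*Protocol*

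**What the plan says.** Protocol 6.9.6 introduces the classification with "The following categories will be used to define the relationship of an AE to the administration of the IMP" and then lists two. For Not Related the condition is "Data are available to identify a clear alternative cause for the AE other than the IMP". For Related it is "The cause of the AE is related to the investigational product and cannot be reasonably explained by other factors"; the examples of other factors are the subject's clinical state, other therapy and other interventions. There is no intermediate category and no instruction for doubtful cases.

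The choice is compulsory: under Protocol 6.9.3 "the Investigator must assess whether the AE is drug-related or not". It is made locally, since 6.9.6 states that the investigator or a qualified sub-investigator "is responsible for determining the AE relationship to the IMP". Neither document describes central review of causality, and Protocol 10.8 rules out a data monitoring committee.

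The field feeds the analysis. Protocol 9.5.1.1 says AE incidence "will be summarized for all AEs, by the relationship to IMP and by severity". SAP 12.1.1 to 12.1.3 count related TEAEs, related SAEs, related TEAEs by maximum severity and related events leading to discontinuation. The SAP has a subheading for treatment-related events but does not define the term, so it inherits the recorded value. Its one default rule, in 20.6, begins "If the relationship is missing for an AE started on or after the date of the first dose" and assigns Related.

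**The concern.** Each definition sets a high bar at its own end of the scale and leaves the middle empty. An investigator who sees nausea or insomnia in a subject with another plausible explanation, but no proof of it, cannot truthfully apply either wording. One box must still be ticked. Two sites following the protocol equally carefully can record the same event differently, and neither would be wrong.

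This matters more than it would in a controlled trial. There is one treatment group (SAP 6.3), safety is the primary analysis (Protocol 9.5), and no comparator arm shows the background rate. The related subset is the plan's main way of separating drug effects from background. Uncertain cases are foreseeable: all subjects have opioid use disorder, urine is screened for several drug classes, and prescribed benzodiazepines may be allowed case by case (Protocol 6.10). Protocol Table 1 describes events in the earlier studies as possibly related, a grade for which the present form has no place.

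**Working it through.** No figure in the plan rests on this point. The 300 subjects come from roll-over eligibility, and no related-AE rate is stated, so there is nothing to reproduce. The check is logical, followed by a bound on the effect.

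**Step 1: do the two definitions cover all cases?** Take three judgements from the wording of 6.9.6:

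- C: data identify a clear alternative cause.
- R: other factors can reasonably explain the event.
- D: the investigator judges the product to be the cause.

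A clear alternative is also a reasonable one, so C implies R. Of 2 × 2 × 2 = 8 combinations, the 2 with C but not R are impossible, which leaves 6. Not Related = C. Related = D and not R.

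| C | R | D | Category under 6.9.6 |
|---|---|---|---|
| yes | yes | yes | Not Related |
| yes | yes | no | Not Related |
| no | no | yes | Related |
| no | yes | yes | neither |
| no | yes | no | neither |
| no | no | no | neither |

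Two rows are Not Related, one is Related, none is both, and three are neither. Two of these three are events with a plausible but unproven alternative. The third is an event with no identified cause that the investigator does not attribute to the drug.

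**Step 2: does another provision place the three empty rows?** Protocol 6.9.3 requires an answer but does not say which. SAP 20.6 acts only on a missing value, and a site complying with 6.9.3 leaves none. No adjudication step is described. With about 300 subjects at up to 31 sites (Protocol 9.2 and 10.1.2), the average is 300/31 = 9.7 subjects per site if all are used, so many separate local habits could be in play.

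**Step 3: what can be said about size?** Let b be the share of subjects with at least one TEAE that clearly meets Related, and g the further share whose only candidates for Related are gap events. The reported related-TEAE rate then lies between b (all gap events recorded Not Related) and b + g (all recorded Related), so the possible swing is g. The documents give neither b nor g. The following values are assumed, with N = 300 and exact 95% intervals:

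| b | g | Lowest rate | Highest rate |
|---|---|---|---|
| 5% | 5% | 15/300 = 5.0% (2.8 to 8.1) | 30/300 = 10.0% (6.8 to 14.0) |
| 10% | 10% | 30/300 = 10.0% (6.8 to 14.0) | 60/300 = 20.0% (15.6 to 25.0) |
| 20% | 20% | 60/300 = 20.0% (15.6 to 25.0) | 120/300 = 40.0% (34.4 to 45.8) |

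The swing in each row is simply the g put in. The table shows how the effect works; it does not estimate it.

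**Step 4: which outputs move?** In the SAP table list these are the related rows of 14.3.1.1, all of 14.3.1.7 (related serious TEAEs) and 14.3.1.9 (related TEAEs by maximum severity), and 14.3.1.10 (severe related TEAEs leading to discontinuation). Total TEAEs, total SAEs, deaths and the special-interest tables do not use the field.

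**The case against.** The case for leaving the text alone has several parts.

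*Sites may be told what to do elsewhere.* Protocol 8.1 and 10.7 promise eCRF completion guidelines and training, which could settle uncertain cases. This is possible, and variation between sites is inferred rather than shown. But the definition belongs in the protocol, and the SAP points to no other rule.

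*The affected output is narrow.* The study is descriptive, no test or sample size depends on the field, and all AEs are listed with their actual values. This stands and limits the weight of the point.

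*Defaulting everything uncertain to Related overshoots.* Two of the three empty rows are events that the investigator does not attribute to the drug. This also stands, as a cost of the fix. It does not remove the need for a rule, because those rows must go somewhere.

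A reader might also infer four stronger things that the documents do not support:

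- *That expedited reporting is compromised.* Under Protocol 6.9.11.2 every SAE goes to the sponsor within 24 hours whatever its cause, and notice to the IRB does not require a causal link. Section 6.9.11.1 defines a SUSAR by its inconsistency with product information and leaves the decision to the sponsor's pharmacovigilance group. The site's causality box appears in none of these rules.
- *That related events will be under-counted.* The strict wording of Related pushes doubtful events out of the related count, but the equally strict wording of Not Related pushes them in. No direction follows.
- *That a size in percentage points can be given.* Any such figure only restates an assumed share of uncertain events, and it also needs every site to resolve them the same way.
- *That blank fields will regularly turn doubtful events into Related through SAP 20.6.* A blank breaches 6.9.3, and the edit checks and queries in Protocol 10.11.1 and 10.11.2 would normally catch it.

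**Conclusion.** The point holds as a defect in a stated rule. The categories in Protocol 6.9.6 are mutually exclusive but not exhaustive: three of six admissible combinations fit neither, and nothing else in the protocol or SAP assigns them. The related-TEAE, related-SAE, related-by-severity and related-discontinuation tables therefore rest partly on local convention and can shift either way. The size cannot be computed from the documents. Total event counts, the SAE and SUSAR reporting rules and the sample size are unaffected. The conclusion assumes that the definitions are applied as written and that no guideline outside these documents already supplies a default.

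**What to change.** Keep the definition of Not Related. Redefine Related in 6.9.6 as any AE for which no clear alternative cause has been identified, including AEs of uncertain cause, and repeat this in the eCRF guideline. In the notation above, Related becomes not C: two rows are Not Related, four are Related, and none is unplaced. This goes in the same conservative direction as the missing-value rule in SAP 20.6. The SAP should then define treatment-related by reference to this rule.

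If events have already been classified, do not recode them silently. State in the SAP and the study report that uncertain cases had no defined category, so that the related-AE tables are read accordingly.

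The text cost is one sentence in the protocol and one in the guideline. The analytical cost is a somewhat higher related-AE rate that includes some events the investigator would not positively attribute to the drug, and a footnote to any comparison with the parent study if that study used another rule.
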